### **3.3 Benefit/Risk Assessment**

At this time, there is limited clinical experience with AMG 420 in humans. Based on nonclinical toxicity studies of AMG 420, and preliminary clinical safety and efficacy experience with AMG 420, the overall benefit/risk profile favors further clinical development of AMG 420 for patients with RRMM. Clinical signs and symptoms, along with other safety laboratory parameters, will be monitored during the study and at the appropriate time points to ensure subjects' safety.

The following benefit risk assessment supports the conduct of this clinical trial. Reference should be made to the [Investigator's Brochure](#) for further data on AMG 420.

---

### 3.3.1 Therapeutic Context

Multiple myeloma treatment has evolved rapidly in recent years. Progress has been made with the introduction of several breakthrough drugs, including IMiDs and PIs, as well as anti-CD38 targeting monoclonal antibodies, which have led to a significant increase in response rate as well as survival rate (Dimopoulos et al, 2016; Palumbo et al, 2016; Kumar et al, 2012). While treatment for multiple myeloma will often induce remission, multiple myeloma is characterized by a recurring pattern of remission and relapse. With each subsequent line of treatment, the duration and depth of response decreases (Cook et al, 2018), and patients eventually develop treatment resistance (Papadas et al, 2017). It is not uncommon for patients to be treated with 3 or more lines of therapy.

The goal of treatment for RRMM is to achieve the longest progression-free survival (PFS) and subsequently overall survival (OS). The depth of response is associated with OS and a critical factor to achieving that goal (Chanan-Khan and Giralt, 2010; Richardson et al, 2007). Additional goals include controlling disease to prevent or delay associated complications (such as bone fractures, renal insufficiency, and infections), maintaining an acceptable health related quality of life, and providing relief of pain and other disease-related symptoms. Investigational agents that utilize both novel targets and mechanisms of action, especially those that have shown clinical activity in first-in-human studies, have the potential to achieve these goals, particularly in patients with a high unmet need after their disease has progressed following treatment with available standard-of-care therapies.

### 3.3.2 Key Benefits

As AMG 420 is still in early development and clinical experience is still limited, key benefits are still being investigated and will be described when the data become available.

### 3.3.3 Key Risks

The target cell populations of AMG 420 are plasma cells, mature and activated B-cells shown to express BCMA; hence the potential on-target toxicity is depletion of these hematologic cell types and immunoglobulin level, which could result in an increased risk of infection.

At this time, there is limited clinical experience with AMG 420 in humans. Based on biological possibility, nonclinical toxicity studies of AMG 420, and clinical safety experience with AMG 420 and other BiTE® antibody constructs in hematology, such as

blinatumomab, the safety risks for AMG 420 include cytokine release syndrome (CRS), infections, and neurologic events (see [Table 3-1](#)).

**Table 3-1. Key Safety Risks for AMG 420**

Safety Risk	Description
Important Identified Risks	
Cytokine Release Syndrome (CRS)	
Cytokine release syndrome (CRS), including serious events, has been reported for patients receiving AMG 420 in the clinical trial setting.
 
Signs and symptoms many include the following:
 

• Constitutional – fever, rigors, fatigue, malaise

• Neurologic – headache, mental status changes, dysphasia, tremors, dysmetria, gait abnormalities, seizure

• Respiratory – dyspnea, tachypnea, hypoxemia

• Cardiovascular – tachycardia, hypotension

• Gastrointestinal – nausea, vomiting, transaminitis, hyperbilirubinemia

• Hematology – bleeding, hypofibrinogenemia, elevated D-dimer

• Skin – rash

Important Potential Risks	
Infections	Infections, including device-/catheter-related infections, have been reported in the clinical trial setting with administration of AMG 420.
Neurologic Events	Neurologic events, including headache and peripheral neuropathy, have been reported in the clinical trial setting with administration of AMG 420.

Clinical signs and symptoms of CRS, infections, and neurologic events, along with other safety labs, will be monitored during the study and at the appropriate time points to ensure subjects' safety. Refer to [Section 7.4.2.1.2](#) for specific recommendations regarding the mitigation and management of CRS, infections, and neurologic events.

Please refer to the AMG 420 [Investigator's Brochure](#) for further description of the key safety risks.

### 3.3.3.1 Risks

Refer to the AMG 420 [Investigator's Brochure](#) for further description of safety risks.

[figure not shown]
**4. Objectives, Endpoints and Hypotheses**

**4.1 Objectives and Endpoints**

Objectives	Endpoints
Phase 1b	
Primary	

 
Establish the safety and tolerability of AMG 420 at dose levels of 400 µg/day and 600 µg/day in subjects with relapsed and/or refractory multiple myeloma (RRMM)
 
	
 
Dose-limiting toxicities (DLTs), treatment-emergent adverse events, treatment-related adverse events, and changes in vital signs, electrocardiograms (ECGs), and clinical laboratory tests
 

Key Secondary	

 
Estimate overall response rate (ORR) and duration of response (DOR) of AMG 420 in subjects with RRMM
 
	
 
ORR
 
DOR
 

 
Evaluate the rate of minimal residual disease (MRD)-negativity at the time of CR
 
	
 
MRD negativity at the time of CR
 

Secondary	

 
Establish the safety and tolerability of AMG 420 in subjects with extramedullary relapsed multiple myeloma
 
	
 
DLTs, treatment-emergent adverse events, treatment-related adverse events, and changes in vital signs, ECGs, and clinical laboratory tests
 

 
Characterize the pharmacokinetics (PK) of AMG 420 when administered as 4-week continuous intravenous (cIV) infusion
 
	
 
AMG 420 PK parameters including, but not limited to, half-life (<math>t_{1/2}</math>), clearance, and apparent <math>C_{ss}</math>
 

Objectives	Endpoints
Secondary	

• Evaluate other measures of anti-myeloma activity of AMG 420 in subjects with RRMM:

– Time to response

– Progression-free survival (PFS)

– Overall survival (OS)

– Best overall response (BOR)

	

• Efficacy parameters according to International Myeloma Working Group (IMWG) response criteria, per investigator assessment:

– Time to response

– PFS

– OS

– BOR

Objectives	Endpoints
Exploratory	

---

## 4.2 Hypotheses

A safe and tolerable dose of AMG 420 will have evidence of anti-tumor activity in patients with relapsed and/or refractory multiple myeloma as measured by the rate of overall response.

The ORR according to IMWG response criteria along with 95% CI will be calculated per investigator assessment for subjects with RRMM. The lower bound of the binomial 2-sided 95% confidence interval for ORR not lower than 35% is considered clinically meaningful.

## 5. Study Design

### 5.1 Overall Design

This is a phase 1b, multicenter, non-randomized, open-label expansion study. AMG 420 will be evaluated in adult subjects with RRMM.

The study will consist of up to a 21-day screening, a treatment period, safety follow-up (SFU), and long-term follow-up (LTFU) period. In the treatment period, treatment will be continued until PD or relapse as defined by IMWG response criteria (see [Section 12.8](#)), unacceptable safety events, next anti-multiple myeloma treatment, or other reason for permanent treatment discontinuation. All subjects will be assessed for anti-myeloma activity according to the IMWG response criteria. An SFU visit will be conducted 30 (+3) days after last administration of AMG 420, and an LTFU period will begin after the SFU visit is completed. The total duration of the LTFU will be up to 5 years from the first dose of AMG 420, or until subject death, whichever is first.

#### 5.1.1 Phase 1b (Monotherapy Dose Confirmation)

In phase 1b, approximately 10 subjects will be treated at the 400 µg/day dose (comprising cohort 1). Approximately 10 subjects will be treated at the 600 µg/day dose level (cohort 2).

The dose level review team (DLRT) will convene and review all available safety, laboratory, and PK data at the following scheduled time points:

- After at least 10 subjects in phase 1b cohort 1 (400 µg/day dose level) have had the opportunity to complete the 4-week infusion period of the first treatment cycle: On the basis of this review, the DLRT will make a recommendation regarding the initiation of phase 1b cohort 2 (600 µg/day dose level).
- After at least 3 subjects with EM relapsed disease in phase 1b cohort 1 (400 µg/day dose level) have had the opportunity to complete the 4-week infusion period of the first treatment cycle: On the basis of this review, the DLRT will make a recommendation regarding the appropriateness of continued enrollment of subjects

with EM relapsed disease in phase 1b cohort 2 (600 µg/day dose level). Please note that enrollment of subjects with EM relapsed disease in phase 1b cohort 2 will not be allowed until this safety review of the first 3 subjects with EM disease is completed by the DLRT.

- After the first 3 subjects have been dosed with AMG 420 at 600 µg/day for the full 4-week infusion cycle in phase 1b cohort 2.

In phase 1b, the safety data will be reviewed on an ongoing basis and enrollment may be terminated at any time. To further reduce the risk of overdose to ongoing and future subjects, protocol-defined enrollment holding rules will be used. These rules are based on a modified Toxicity Probability Interval (mTPI) (Ji et al, 2010) where the target TPI is a DLT probability from 20% to 33% and the overdose TPI is > 33% DLT probability. Enrollment to the ongoing dose level/schedule will be paused per the rules in [Table 5-1](#) during enrollment into phase 1b cohorts 1 and 2.

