4.2 Subgroups

The baseline variables for the subgroup analyses may include:

- baseline demographics and characteristics:
 - age (< 65, 65-74, ≥ 75 years)
 - sex (female, male)
 - race (White, Asian, other)
- baseline disease characteristics:
 - revised International Staging System (ISS) stage (Stage I, Stages II or III)
 - BM percent of plasma cells (< 50%, ≥ 50%)
 - 
 - extramedullary disease (yes, no). Until safety evaluation is complete for 3 subjects with EM disease, imaging evaluation at screening will be used to document EM disease status.
- number of prior lines of therapy (only 3, > 3)

- prior allogeneic HSCT (yes, no)
- refractory to
 - IMiD (yes, no)
 - PI (yes, no)
 - IMiD + PI (yes, no)
 - daratumumab or other CD 38-targeting antibody (yes, no)

Subgroup analysis will not be performed due to each sub group may not have justifiable count as less number of sample size.

5. Definitions

Adverse Event (AE)

An adverse event is defined as any untoward medical occurrence in a clinical trial subject. The event does not necessarily have a causal relationship with study treatment. The definition of adverse events includes worsening of a preexisting medical condition. A preexisting condition that has not worsened during the study, or involves an intervention, is not considered an adverse event.

Age at Enrollment

Subject age at enrollment will be determined using the age in years reported in the clinical database.

Baseline

For any variable, unless otherwise specified the baseline is the last assessment taken prior to the first administration of AMG 420. For parameters/assessments not scheduled to be performed (or scheduled but not performed) on the same day as the first administration of AMG 420, the baseline value is the value from the screening period measured closest to the day of first administration of AMG 420.

Baseline ECG Values in Triplicate

For the three sets of triplicate pre-dose ECG, the mean of values in a triplicate should be calculated before taking the mean of the three sets of averages. For all post-baseline ECG, the mean value for measurements taken at the same assessment will be calculated and used in the analysis. When an ECG is missing within a triplicate, all available data will be averaged for that time point.

Death Date

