9.6.2 Adverse Events

The Medical Dictionary for Regulatory Activities (MedDRA) version 23.0 or later will be used to code all adverse events to a system organ class and a preferred term. The severity of each adverse event will be graded using CTCAE version 5.0 criteria with exception of CRS which will be graded according to adopted grading system in Lee et al, 2014 and TLS graded according to Cairo-Bishop criteria (refer to protocol Appendix 12). Where appropriate the tables will also be presented by worst grade.

Treatment-emergent adverse events will be summarized based on the number (%) of subjects experiencing events by MedDRA SOC and PT. The denominator for the percentage will be based on the number of subjects in the safety analysis set.

The subject incidence of adverse events will be summarized for

- **TEAE**
 - All treatment-emergent AEs
 - Grade 3 or higher treatment-emergent AEs
 - Treatment-emergent SAEs
 - Treatment-emergent AEs leading to interruption of investigational product
 - Treatment-emergent AEs leading to withdrawal of investigational product
 - Fatal treatment-emergent AEs
- **Treatment-related AEs**
 - All treatment-related AEs
 - Grade 3 or higher treatment-related AEs
 - Treatment-related SAEs
 - Treatment-related AEs leading to interruption of investigational product
 - Treatment-related AEs leading to withdrawal of investigational product
 - Fatal treatment-related AEs

The summaries that are displayed by SOC, PT and grade will be ordered by descending order of incidence of SOC, PT and grade with in each SOC for the total group.

Then summary of TEAEs, summary of TEAEs, TESAEs, Treatment-related TEAEs, and Treatment-related SAEs by SOC, PT and Grade will be generated for extramedullary subjects.

The above adverse event tables will not be created if two or fewer subjects experience the adverse event.

Dose Limiting Toxicities

The analysis of the probability of DLTs will include data from DLT-evaluable subjects (see Protocol Section 7.4.1 for definition of DLT-evaluable). The primary analysis will only include DLTs that occur during the DLT evaluation period. If DLTs occur outside the DLT evaluation period, a sensitivity analysis will be performed where DLTs occurring outside of the specified time interval are included. The number and percentage of subjects reporting DLTs will be evaluated overall and by AMG 420 dose level.

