9.7.5 Analyses of Biomarker Endpoints

The analysis of Biomarker will be described and performed by Clinical Biomarker Group.

10. Changes From Protocol-specified Analyses

There are no changes to the protocol-specified analyses.

11. Literature Citations / References

12. Prioritization of Analyses

No Priority of outputs planned for this study

13. Data Not Covered by This Plan

The analysis of Biomarkers (except MRD) is not covered in this plan.

14. Appendices

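### Safety in extramedullary disease is a stated objective, but the SAP gives EM subjects adverse event summaries only, and no rule secures the 3 EM subjects that the planned EM review needs

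*Protocol*

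**What the plan says.** **Objective.** Protocol 4.1 and SAP 2.1 make safety in EM relapsed myeloma a secondary objective. No dose is named. Its endpoints are "DLTs, treatment-emergent adverse events, treatment-related adverse events, and changes in vital signs, ECGs, and clinical laboratory tests". Protocol 5.4 adds that one primary purpose of the phase is to confirm 400 µg/day in subjects with or without EM disease.

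**Enrollment.** Protocol 5.1.1 states: "In phase 1b, approximately 10 subjects will be treated at the 400 µg/day dose". A similar number is planned at 600 µg/day (cohort 2). The review on which the start of cohort 2 depends is due "After at least 10 subjects in phase 1b cohort 1 (400 µg/day dose level) have had the opportunity to complete the 4-week infusion period" of cycle 1, whatever their EM status. A separate review needs at least 3 EM subjects from cohort 1. Entry of EM subjects to cohort 2 "will not be allowed until this safety review of the first 3 subjects with EM disease is completed by the DLRT".

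**Analysis.** SAP 9.6.2 ends its EM outputs with "Treatment-related SAEs by SOC, PT and Grade will be generated for extramedullary subjects". All of the EM outputs in that sentence are adverse event summaries. The same section then says that its adverse event tables are not produced when no more than two subjects have the event. SAP 4.2, whose list of subgroup variables includes EM disease, says: "Subgroup analysis will not be performed due to each sub group may not have justifiable count". SAP Section 10 says: "There are no changes to the protocol-specified analyses".

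**The concern.** There are two gaps, and they compound. First, the EM objective lists more endpoints than the SAP reports for EM subjects. A team following the SAP as written would finish without an EM DLT count and without EM output for vital signs, ECGs or laboratory tests. Second, the EM review depends on 3 cohort 1 subjects whom nothing in the plan secures. If cohort 1 fills with 0 to 2 of them, cohort 2 can still open, EM subjects stay barred from it, and no text says what happens next. The study could then have no EM data at 600 µg/day and very little at 400 µg/day, in the situation where the SAP's table rule also removes the EM adverse event tables.

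**Working it through.** **Step 1. EM endpoints set against SAP outputs.**

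| EM endpoint (Protocol 4.1) | Output for EM subjects in the SAP |
|---|---|
| Treatment-emergent AEs | Yes, 9.6.2 |
| Treatment-related AEs | Yes, 9.6.2 |
| DLTs | None by EM status; 9.6.2 reports DLTs overall and by dose level |
| Laboratory changes | None in 9.6.3 |
| Vital sign changes | None in 9.6.4 |
| ECG changes | None in 9.6.6 |

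Two of six endpoints have a planned EM output. This needs no assumption.

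**Step 2. The two-or-fewer rule.** With 0, 1 or 2 EM subjects, no event can occur in more than 2 of them, so applied to the EM tables the rule removes all of them. With exactly 3 EM subjects, applied event by event, it keeps only events that all 3 had.

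**Step 3. Search for a rule that secures 3 EM subjects.** Protocol 5.2 (number of subjects), 6.1 (inclusion), 6.3 (enrollment and allocation) and 10.1 (sample size) contain no EM minimum, and no fallback is stated.

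**Step 4. The plan's own figure.** Protocol 10.1 gives a 65% to 89% chance of seeing an adverse event in 10 subjects at true rates of 10% to 20%. The formula is 1 − (1 − p)^10. It gives 1 − 0.9^10 = 0.651 and 1 − 0.8^10 = 0.893, so the figure reproduces.

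**Step 5. Chance of missing the EM trigger.** Inputs: n = 10 (Protocol 5.1.1) and trigger = 3 (same section). The EM share p is not in the documents and is an assumption. With unselected accrual,

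P(fewer than 3) = (1 − p)^10 + 10p(1 − p)^9 + 45p²(1 − p)^8.

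At p = 0.20: 0.107 + 0.268 + 0.302 = 0.678 (terms rounded).

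| Assumed EM share | P(fewer than 3 of 10) | P(fewer than 3 of 12) |
|---|---|---|
| 10% | 0.930 | 0.889 |
| 20% | 0.678 | 0.558 |
| 30% | 0.383 | 0.253 |
| 40% | 0.167 | 0.083 |
| 50% | 0.055 | 0.019 |

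For a 90% chance of at least 3 EM subjects, unselected accrual would need 52, 25, 16 or 12 subjects in cohort 1 at shares of 10%, 20%, 30% or 40%.

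**Step 6. What 3 subjects can show.** The chance of at least one event is 1 − 0.9^3 = 27% to 1 − 0.8^3 = 49% at true rates of 10% to 20%. With 0 events in 3, the exact two-sided 95% upper limit is 1 − 0.025^(1/3) = 71%. Even when the trigger is met, EM results will be individual data rather than a rate estimate, so listings are the right format.

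**The case against.** The strongest reply is that little is lost in practice, and much of it stands.

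- A reader might infer that the objective is blocked. The documents do not support that. The objective names no dose, and EM subjects may enter cohort 1 from the start. The bar is a safety rule, and having no EM data at 600 µg/day when EM experience at 400 µg/day is thin is a consistent result of it.
- A reader might infer that a short cohort 1 caps the study at 2 EM subjects. That does not follow either. Cohort 1 is approximate, its review needs at least 10, Protocol 5.2.1 allows replacement of non-evaluable subjects, and Protocol 6.3 has the sponsor allocate subjects to cohorts. Nothing says that cohort 1 closes when cohort 2 opens. The sponsor could direct EM subjects to cohort 1, but no rule requires it.
- A reader might infer that four EM endpoints go wholly unreported. Protocol 10.4.2.3.1 provides per-subject listings of laboratory and vital sign data and a listing of all on-study ECG data, and SAP Section 10 declares no departure. DLTs are by SAP definition a subset of treatment-emergent events, so they would fall within the EM event summaries, though not identified as DLTs. What is missing is the EM DLT count and any EM flag or grouping of the other data.
- The exclusion in SAP 4.2 might be read as cancelling EM safety work. It does not, because SAP 9.6.2 still plans the EM summaries. Protocol 10.2.3 ties subgroup analyses to efficacy, allows them to be dropped for small numbers, and commits separately to reviewing EM safety.
- The rationale for Amendment 5 cites termination of the program and no further drug supply. A recruitment change may therefore be moot. The SAP change would not be.

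**Conclusion.** The point holds in two parts of different strength. The analysis gap is certain from the text: four of the six EM endpoints have no EM-specific output in the SAP, and the two-or-fewer rule, applied to the EM tables, would remove them if 0 to 2 EM subjects enrol. The enrollment gap is a possibility. No rule secures 3 EM subjects in cohort 1 or covers a shortfall, but the chance of one runs from about 5% to 93% over assumed EM shares of 50% down to 10%. A reader might take the upper part of that range as showing that failure is likely. The documents give no EM share, so they do not support that. The figures also assume unselected accrual and a fixed cohort of 10, both of which the sponsor could alter.

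**What to change.** **SAP 9.6, whatever the enrollment status.** For EM subjects, by dose cohort, add a DLT count and listing, and EM-flagged listings of vital sign, ECG/QTcF and laboratory changes. Exempt the EM adverse event outputs from the two-or-fewer rule, using listings where numbers are too small for a table. The cost is small, as existing programs can be reused with an EM flag.

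**Protocol 5.1.1 and 6.3, if enrollment is still open.** Hold 3 of the approximately 10 cohort 1 places for subjects with EM disease on screening imaging, and state a time limit or fallback if they are not found. Protocol 9.2.2.6 already requires that imaging for everyone, and the sponsor already confirms eligibility and allocates cohorts. The review rule, the doses and the total sample size stay as they are. The downside is that cohort 1 may fill more slowly. This part is more debatable than the SAP change.

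**If enrollment has closed.** Report the number of EM subjects per cohort, and limit the EM safety conclusion to the doses at which they were treated.
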